4 SAMPLE SIZE CONSIDERATIONS

Approximately 60 subjects evaluable for efficacy will be enrolled: approximately 40 in Stage 1 and 20 in Stage 1b. Non-evaluable subjects will be replaced.

4.1 Sample Size Determination for Stage 1

The goal of Stage 1 is to establish if this pracinostat + azacitidine regimen is safe and tolerable, as measured by the rate of treatment discontinuation due to possibly safety related reasons in the first 3 cycles of therapy. An discontinuation rate of 10%, based on that was observed in the azacitidine + placebo group in Study MEI-003 will be used as the threshold for safety evaluation. The 95% CI approach is utilized to estimate the sample size in Stage 1. A rate of treatment discontinuation of 22.5%, the midpoint between the discontinuation rates in the azacitidine + placebo (10%) and azacitidine + pracinostat (32%) groups, respectively, in Study MEI-003, is assumed to be the estimated discontinuation rate due to possibly safety related reasons.

With a sample size of 40 subjects, the study will be stopped if ≥ 9 subjects (22.5%, 95% CI: 10.8–38.4%) discontinue in the first 3 cycles. Under this scenario, the lower bound of the 95% CI is $> 10\%$ (above the pre-specified desired goal).

In addition to the discontinuation threshold, the lower bound of 95% CI for an observed ORR of $\geq 25\%$ will be desired to support opening Stage 1b of the study because it is expected that azacitidine alone results in an ORR of approximately 25% in high/very high-risk MDS. For example, with a sample size of $N=40$ and an assumed ORR of 45% for the azacitidine + pracinostat combination regimen, the 95% CI using exact method is (29.3%, 61.5%) with the lower bound higher than 20%.

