- In prior studies in MDS and AML, approximately 50% of subjects who achieved an objective response and received pracinostat for more than one year had their dose reduced from 60 mg to 45 mg, indicating this dose is efficacious and well tolerated.
- A dose of 40 mg was shown to induce a 2-fold increase in histone 3 acetylation (acH3) in 17 subjects with solid tumors, a level comparable to that achieved with a dose \geq 60 mg but significantly higher than achieved with a dose of 20 mg, suggesting that a dose of 45 mg may be sufficient for full pharmacodynamic effects.
- A dose of 45 mg results in plasma concentrations greater than HDAC C1 inhibitory constant (Ki) for approximately 24 hours, suggesting adequate HDAC inhibition at this dose.

STUDY DESIGN

This is a Phase 2, two-stage study of the safety and efficacy of pracinostat in combination with azacitidine in patients with IPSS-R high and very high-risk MDS who are previously untreated with HMAs. Enrollment in this study will be limited to high/very high-risk MDS because this group represents the highest unmet need, with median survival of less than 18 months. Recognizing that additional safety and efficacy of pracinostat plus azacitidine is desirable before evaluating the treatment regimen in a placebo-controlled environment, the protocol is being amended to become a 2-stage open-label study comprising Stage 1 and Stage 1 expansion (Stage 1b).

Stage 1 will be conducted as an open-label single arm in approximately 40 evaluable subjects to assess if this regimen with a lower pracinostat dose results in a discontinuation rate that meets a predefined threshold and the observed efficacy justifies expansion to Stage 1b.

A discontinuation rate of approximately \leq 10% in Stage 1, a rate comparable to that observed with azacitidine alone in Study MEI-003, would support expansion to Stage 1b. Stage 1b will be conducted as an open-label, single-arm to achieve a total enrollment of approximately 60 efficacy evaluable subjects, inclusive of Stage 1 and Stage 1b enrollment.

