The Independent Data Monitoring Committee (IDMC), in coordination with the Sponsor, will determine when to open Stage 1b enrollment.

Total sample size calculation

Approximately 60 subjects evaluable for efficacy will be enrolled in the study: approximately 40 in Stage 1 and 20 in Stage 1b. An ORR of 40% in subjects with high/very high-risk MDS treated with pracinostat plus azacitidine will be considered a clinically meaningful improvement compared to a historical ORR of 25% with azacitidine alone in this subject population. With a sample size of 60 subjects, the lower limit of the 95% CI of an observed ORR of 40% is 27.6%, higher than the ORR anticipated with azacitidine alone, and will support continued evaluation of this treatment regimen in a larger study.

Statistical Analysis

All analyses will be descriptive. Binomial variables will be presented as frequency and 95% CI. Continuous variables will be presented as median, mean, range, and 95% CI. Time-to-event endpoints will be analyzed by the method of Kaplan-Meier. Comparisons between subject subsets will be exploratory.

Primary and exploratory analyses will be performed as described in detail in the study Statistical Analysis Plan.

TABLE OF CONTENTS

TITLE	1
PROTOCOL SIGNATURE PAGE	2
INVESTIGATOR SIGNATURE PAGE	3
SYNOPSIS	4
TABLE OF CONTENTS	12
LIST OF TABLES	14
LIST OF ABBREVIATIONS	15
1 INTRODUCTION	18
1.1 Background	18
1.2 Pracinostat	18
1.3 Preclinical Pharmacology	18
1.4 Clinical Experience	18
1.5 Rationale for the Study	19
1.6 Rationale for Pracinostat Dose Selection	21
1.7 Rationale for Patient Population	21
2 STUDY OBJECTIVES	21
2.1 Primary Objectives	21
2.2 Secondary Objectives	22
3 STUDY DESIGN	22
3.1 Treatment Plan	23
3.1.1 Pracinostat	23
3.1.2 Azacitidine	24
4 SUBJECT POPULATION AND DISCONTINUATION CRITERIA	24
4.1 Inclusion Criteria	24
4.2 Exclusion Criteria	25
4.3 Discontinuation from Study Treatment	27
5 STUDY PROCEDURES AND ASSESSMENTS	27
5.1 Screening	28
5.2 Study Treatment	29
5.2.1 Day 1, All Cycles	29
5.2.2 Days 2–9, All Cycles	30
5.2.3 Day 15 and Day 22 (Cycles 1 and 2 only)	30
5.2.4 Response Assessments	30
5.3 End of Treatment	32
5.4 Follow-up	32
5.5 End of Study	32
5.6 Cytogenetic and Molecular Studies	33
6 SAFETY	33
6.1 Adverse Events	33
6.1.1 Definitions of Adverse Events	33
6.1.2 Recording and Reporting of Adverse Events	33
6.1.3 Handling of Adverse Events	34
6.2 Serious Adverse Events	35
6.2.1 Definitions of Serious Adverse Events	35

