9 STATISTICAL PLAN

9.1 Sample Size

Approximately 60 subjects evaluable for efficacy will be enrolled: approximately 40 in Stage 1 and 20 in Stage 1b. Non-evaluable subjects will be replaced.

9.1.1 *Sample Size Calculation for Stage 1*

The goal of Stage 1 is to establish if this pracinostat + azacitidine regimen achieves a discontinuation rate of approximately $\leq 10\%$ in the first 3 cycles of therapy, a rate comparable to that achieved in the azacitidine + placebo group in Study MEI-003. The 95% CI approach is utilized to estimate the sample size in Stage 1. The number of subjects to be enrolled is calculated such that the lower bound of the 95% CI of the discontinuation rate will be no more than 12% lower than the point estimate of 22.5%, the midpoint between the discontinuation rates in the azacitidine + placebo (10%) and azacitidine + pracinostat (32%) groups, respectively, in Study MEI-003.

With a sample size of 40 subjects, the study will be stopped if ≥ 9 subjects (22.5%, 95% CI: 10.8–38.4%) discontinue in the first 3 cycles. Under this scenario, the lower bound of the 95% CI is > 10 % (above the pre-specified desired goal) and the upper bound of the 95% CI is > 32 % (higher than the discontinuation rate in study MEI-003).

It is also possible to conclude that the desired threshold of a discontinuation rate of ≤ 10 % has been achieved with fewer than 40 subjects treated in Stage 1. For example, if 4 discontinuations are observed in the first 32 subjects, the lower and upper bounds of the 95% CI around the observed discontinuation rate of 12.5% (4 of 32) are 3.5% and 29.0%, lower than reported with azacitidine/placebo and azacitidine/pracinostat, respectively, in Study MEI-003. This would justify expanding enrollment to Stage 1b of the study after only 32 subjects have been treated for ≥ 3 cycles.

In addition to the discontinuation threshold, an observed ORR of ≥ 20 % will be desired to support opening Stage 1b of the study because it is expected that azacitidine alone results in an ORR of approximately 20% in high/very high-risk MDS.

The study's Independent Data Monitoring Committee (IDMC), in coordination with the Sponsor, will determine when enrollment in Stage 1 can be concluded, and whether to open enrollment in Stage 1b.

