9.1.2 Total Sample Size Calculation

This study is intended to provide preliminary efficacy information to serve as a basis for a subsequent confirmatory study. Published studies have reported an ORR of approximately 25% (range 20-32%) with azacitidine alone in higher risk MDS ([Fenaux 2009](#), [Prebet 2014](#), [Sekeres 2014](#)). An ORR of 40% with pracinostat plus azacitidine will be considered as clinically meaningful improvement compared to azacitidine alone. With a sample of 60 subjects, the lower bound of the 95% CI of an observed ORR of 45% is 27.6%, higher than the expected ORR with azacitidine alone, and will support continued evaluation of pracinostat plus azacitidine in a larger study in higher risk MDS. Table 2 lists the lower bound of the 95% CI for a range of ORR and indicates that a sample of 60 subjects is informative for future development and shows that doubling the sample size to 120 subjects will only increase the precision of the 95% CI by approximately 4%.

Table 2 Lower Bound of the 95% Confidence Interval for a Range of Overall Response Rate

ORR	Lower Bound 95% CI of ORR	
	N = 60	N = 120
50%	36.8	40.7
45%	32.1	35.9
40%	27.6	31.2
35%	23.1	26.5
30%	18.9	22.0

CI = confidence interval; ORR = overall response rate.

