3 STUDY DESIGN

3.1 Overall Study Design

This study is a two stage Phase 2 trial in subjects with IPSS-R high and very high risk myelodysplastic syndromes (MDS) previously untreated with hypomethylating agents.

Stage 1 is an open-label portion in approximately 40 evaluable subjects will be treated with pracinostat and azacitidine. The goal of Stage 1 is to evaluate treatment tolerability – based on whether the combination regimen of pracinostat and azacitidine’s rate of treatment discontinuation due to possibly safety reasons in the first 3 cycles of therapy is not significantly higher than 10%, and to determine if the observed efficacy justifies expansion of enrollment in Stage 1b based on ORR.

Stage 1b is an open-label expansion to achieve a total enrollment of approximately 60 subjects evaluable for efficacy, inclusive of Stage 1 and Stage 1b enrollment.

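### The response-rate criterion for opening Stage 1b differs between Protocol 9.1.1 and SAP 4.1, and SAP 4.1 checks its own example against a different benchmark

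*SAP*

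**What the plan says.** Both documents make Stage 1 efficacy a condition for expansion. The Protocol Synopsis asks whether "the observed efficacy justifies expansion to Stage 1b" and gives no number. SAP 3.1 sets as a goal "to determine if the observed efficacy justifies expansion of enrollment in Stage 1b based on ORR", also without a number.

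Numbers appear in two places only:

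- **Protocol 9.1.1** desires an observed ORR of at least 20% "to support opening Stage 1b of the study because it is expected that azacitidine alone results in an ORR of approximately 20" percent in high/very high-risk MDS.
- **SAP 4.1** begins "In addition to the discontinuation threshold, the lower bound of 95% CI for an observed ORR of" at least 25%, and justifies this with "to support opening Stage 1b of the study because it is expected that azacitidine alone results in an ORR of approximately 25" percent. Its example takes 40 subjects and an ORR of 45%, and says the exact interval "is (29.3%, 61.5%) with the lower bound higher than 20" percent.

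Elsewhere the protocol's benchmark for azacitidine alone is 25%. The Synopsis calls 40% a meaningful improvement "compared to a historical ORR of 25% with azacitidine alone in this subject population". Protocol 9.1.2 says "Published studies have reported an ORR of approximately 25% (range 20-32%) with azacitidine alone in higher risk MDS", and SAP 4.2 repeats that figure.

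SAP 13, which records changes from the protocol, covers the overall survival definition and the analysis populations. It does not mention the Stage 1b criterion.

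**The concern.** The two sentences are nearly the same, but the SAP changes both the statistic (from a point estimate to a lower confidence bound) and the benchmark (from 20% to 25%). The SAP paragraph then compares its example with 20%, so it disagrees with itself as well as with the protocol. The protocol also uses 20% in 9.1.1 and 25% in the Synopsis for the same high/very high-risk population.

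Stage 1 is open-label, and under Protocol 9.4 the sponsor makes the final decision after committee advice. If the Stage 1 responder count meets the protocol's bar but not the SAP's, nobody reading the two documents could say whether the pre-specified efficacy condition was met.

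**Working it through.** **Inputs.** Stage 1 size of about 40 (Protocol 9.1, SAP 4). Benchmarks of 20% (Protocol 9.1.1) and 25% (SAP 4.1). Exact method (named in SAP 4.1 and used for ORR in SAP 9.1). Clinically meaningful ORR of 40% (Synopsis, Protocol 9.1.2, SAP 4.2).

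**Formula.** For x responders of n, the exact (Clopper-Pearson) 95% bounds are: lower = 2.5th percentile of Beta(x, n − x + 1); upper = 97.5th percentile of Beta(x + 1, n − x).

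**The plan's own figure.** 45% of 40 is 18 responders. The exact interval is 29.26% to 61.51%, which matches the SAP's 29.3% to 61.5%. The bound clears both 20% and 25%, so the example passes either way. The interval is right; the benchmark it is compared with is not the one in the preceding sentence.

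**Readings of the SAP sentence.** As written it supports three:

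- The lower bound must be at least 25%. This is closest to how the Synopsis and SAP 4.2 compare a lower bound with the azacitidine rate.
- The observed ORR must be at least 25%.
- The lower bound must exceed 20%. This rests only on the example.

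**Responders needed at n = 40.**

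| Criterion | Responders | Observed ORR | Exact lower bound | One fewer |
|---|---|---|---|---|
| Protocol: observed ≥ 20% | 8 | 20.0% | 9.1% | 7/40 = 17.5% |
| SAP: observed ≥ 25% | 10 | 25.0% | 12.7% | 9/40 = 22.5% |
| SAP: bound > 20% | 14 | 35.0% | 20.6% | 13/40, bound 18.6% |
| SAP: bound ≥ 25% | 17 | 42.5% | 27.0% | 16/40, bound 24.9% |

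The criteria are nested: any count that meets a SAP reading also meets the protocol. The documents disagree only at 8–9, 8–13 or 8–16 responders respectively.

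**Chance of meeting the ORR criterion alone**, from the binomial tail P(X ≥ r) with n = 40:

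| Responders required (r) | True ORR 25% | True ORR 40% |
|---|---|---|
| 8 | 81.8% | 99.8% |
| 10 | 56.1% | 98.4% |
| 14 | 10.3% | 78.9% |
| 17 | 1.2% | 43.2% |

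**Chance of landing in the conflict range**, P(X ≥ 8) − P(X ≥ r):

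| Conflict range | True ORR 25% | True ORR 40% |
|---|---|---|
| 8–9 | 81.8 − 56.1 = about 26% | 99.8 − 98.4 = about 1.4% |
| 8–13 | 81.8 − 10.3 = about 71% | 99.8 − 78.9 = about 21% |
| 8–16 | 81.8 − 1.2 = about 81% | 99.8 − 43.2 = about 57% |

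These are chances that the documents disagree about the ORR criterion, not that the expansion decision changes.

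**Sensitivity to Stage 1 size.** Counts are in the order of the first table.

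| n | Responders needed |
|---|---|
| 38 | 8, 10, 14, 16 |
| 40 | 8, 10, 14, 17 |
| 42 | 9, 11, 15, 17 |
| 32 | 7, 8, 12, 14 |

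The 32-subject row is included because Protocol 9.1.1 allows that expansion could be justified at that point. That passage argues from the discontinuation rate alone, and SAP 4.1 does not carry the option over.

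**A separate slip nearby.** Protocol 9.1.2 attaches a lower bound of 27.6% at 60 subjects to an ORR of 45%. Recomputed, 24/60 (40%) gives 27.6% and 27/60 (45%) gives 32.1%. Its own Table 2, the Synopsis and SAP 4.2 all agree with the recomputation. This does not affect the Stage 1b criterion.

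**The case against.** The strongest reply is that this is a soft criterion. Both documents say only that the result is desired, SAP 11.2 plans no formal interim analysis, SAP 6.5 plans no hypothesis testing, and the committee only advises. Stage 1b adds about 20 subjects to the same single-arm estimate. All of that stands and limits the consequence. It does not make the two sections agree.

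The SAP sentence is also garbled, and the size of the gap depends on the reading. The practical effect runs from small (8–9 responders) to large (8–16), which is why all three readings are shown. The documents do not settle which was meant, but a mismatch remains under each.

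SAP 13 concerns changes to the analysis, and opening Stage 1b is arguably a conduct decision. That has some force. Still, the SAP restates the protocol's criterion with a different statistic and a different number, and section 13 is where a reader would look for that.

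The 40% figure belongs to the 60-subject calculation and is not a Stage 1 bar. True; the 16/40 comparison only shows how demanding one reading is. Stage 1 is also counted in evaluable subjects with replacement, while the intent-to-treat population is all treated subjects. Neither document says which denominator the criterion uses, so a fixed count needs that stated too.

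Finally, a separate committee charter, not among these documents, may hold a working rule. It would not remove the inconsistency here.

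**Conclusion.** The concern holds. Protocol 9.1.1 and SAP 4.1 set different ORR criteria for opening Stage 1b, SAP 4.1 is inconsistent within one paragraph, and no other section resolves it. At 40 subjects the protocol needs 8 responders and the SAP 10, 14 or 17. These counts assume exact two-sided 95% intervals and exactly 40 subjects in the denominator; they shift by at most one between 38 and 42. The point should be fixed, but its reach is modest: it affects whether a reader can tell which efficacy bar for expansion was pre-specified, not any error rate of the final descriptive analysis.

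**What to change.** Put one criterion in both Protocol 9.1.1 and SAP 4.1:

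- one statistic, either the observed ORR or the lower 95% bound;
- one azacitidine benchmark, consistent with the 25% in the Synopsis, Protocol 9.1.2 and SAP 4.2, or a stated reason for using 20% at this point;
- the analysis population and the resulting responder count for the actual Stage 1 size.

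Make the SAP example test that same bar, and list any remaining departure from the protocol in SAP 13. If a lower bound of at least 25% is kept, say openly that it needs 17/40 and that 16/40 misses. If the committee charter states the criterion, bring it into line. Separately, change 45% to 40% beside the 27.6% bound in Protocol 9.1.2.

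The cost is wording in Protocol 9.1.1 and 9.1.2 and SAP 4.1 and 13, with no extra subjects or data. Changing the protocol text means an amendment submitted to the ethics committee under Protocol 10.2. Aligning SAP 4.1 to the protocol would avoid that, but would leave the protocol's own 20% and 25% benchmarks unreconciled.

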4.2 Total Sample Size Determination

This study is intended to provide preliminary efficacy information to serve as a basis for a subsequent confirmatory study. Published studies have reported an ORR of approximately 25% (range 20-32%) with azacitidine alone at higher risk of MDS ([2], [4], [5]). An ORR of 40% with pracinostat plus azacitidine will be considered as clinically meaningful improvement compared to azacitidine alone. With a sample of

60 subjects, the lower bound of the 95% CI of an observed ORR of 40% is 27.6%, higher than the expected ORR with azacitidine alone, and will support continued evaluation of pracinostat plus azacitidine in a larger study in high risk MDS. The table below lists the lower bound of the 95% CI for a range of ORR and indicates that a sample of 60 subjects is informative for future development and shows that doubling the sample size to 120 subjects will only increase the precision of the 95% CI by approximately 4%.

ORR	Lower Bound 95% CI of ORR	
	N=60	N=120
50%	36.8	40.7
45%	32.1	35.9
40%	27.6	31.2
35%	23.1	26.5
30%	18.8	22.0

5 ANALYSIS POPULATIONS

5.1 Safety Population

The Safety Population is defined as all subjects who have been treated. The Safety population will be used for safety analyses.

5.2 Intent to Treat (ITT) Population

The Intent to Treat (ITT) population is defined as all enrolled subjects and is identical to the Safety Population. In this open-label single arm study, subjects who received at least one dose of study drug are defined as enrolled. The ITT population will be used for efficacy analyses.

5.3 Efficacy Evaluable (EE) Population

The Efficacy Evaluable (EE) population for endpoints requiring both bone marrow and peripheral blood assessments is defined as all subjects who

- received at least 2 cycles of therapy and a follow-up bone marrow AND peripheral blood assessments
- or experienced PD prior to completion of 2 cycles of therapy.

The Efficacy Evaluable (EE) population for endpoints requiring either bone marrow or peripheral blood assessment is defined as all subjects who

- received at least 2 cycles of therapy and a follow-up bone marrow OR peripheral blood assessments depending on the corresponding endpoints

or experienced PD prior to completion of 2 cycles of therapy.

The EE population will be used for key efficacy analyses as supportive analyses.

5.3 Per Protocol (PP) Population

The Per Protocol (PP) population is defined as all treated subjects without major protocol deviations, as detailed in section 8.3. The PP population will be used for the primary efficacy analysis.

6 CONSIDERATIONS FOR DATA ANALYSIS

6.1 Programming Environment

All analyses will be conducted using SAS® version 9.3 or above.

6.2 Strata and Covariates

There are no planned strata or covariate-adjusted analyses.

6.3 Subgroups

The following analyses will be broken down overall as well as by risk factor (high vs. very high risk group by IPSS-R), baseline characteristics (Age: <65 vs 65+, Gender, Bone marrow blasts <5% vs ≥5%), primary vs. secondary MDS (secondary MDS is defined as MDS in patients treated with chemo or radiation for a prior malignancy), and undergoing transplant (yes vs no):

Overall Response
Clinical Benefit
Event Free Survival
Overall Survival

6.4 Multiple Comparisons and Multiplicity

There are no planned adjustments for multiple hypothesis testing.

6.5 Significance Level

No formal hypothesis testing is planned.

6.6 Statistical Notation and Methodology

Unless stated otherwise, the term “descriptive statistics” refers to the number of subjects (n), mean, median, standard deviation (SD), minimum (min), and maximum (max) for continuous data and frequencies (counts and percentages) for categorical data. Min and max values will be rounded to the precision of the original value, means and medians will be rounded to 1 decimal place greater than the precision of the original value, and STDs will be rounded to 2 decimal places greater than the precision of the original value. Percentages will be rounded to the nearest whole number (zeros will not be displayed), with values of “<1%” and “>99%” shown as necessary for percentages falling near the boundaries. P-values will be presented with 3 decimal places of precision, and values less than 0.001 will be presented as “<0.001”.

Unless otherwise noted, all data collected during the study will be included in subject data listings and will be sorted by dose cohort, subject number, and date/time within each subject.

7 DATA HANDLING METHODS

7.1 Visit Windows

Day 1 will be the date corresponding to the first administration of study drug.

The screening assessments and the treatment/post-treatment assessments will be partitioned into the following two visit windows:

- A screening window, beginning on Day -14 and ending on Day -1.
- A treatment window, beginning on Day 1 and ending on the Study Day corresponding with the End of Study (EOS) visit.

Subject visits will be presented according to the nominal visit as obtained upon the eCRF. All values will be included in the subject data listings.

